1. TITLE PAGE

| | |
|---------------------------------|---|
| Study Title: | A Multi-Center, Randomized, Double Masked, Placebo Controlled Clinical Study to Assess the Safety and Efficacy of BRM421 Ophthalmic Solution in Subjects with Dry Eye using a Controlled Adverse Environment (CAE®) Model |
| Investigational Product: | BRM421 Ophthalmic Solution |
| Indication Studied: | Dry Eye Syndrome (DES) |
| Brief Description: | This is a multi-center, double-masked, randomized, vehicle-controlled, phase 2 CAE study in approximately 150 subjects. (75 per treatment arm). |
| Name of the Sponsor: | BRIM Biotechnology, Inc. [name] |
| Protocol Identification: | BRM421-16-C001-PR amendment 1,03 February 2017 |
| Development Phase: | 2 |
| Study Initiated: | 07 February 2017 (first subject first visit) |
| Study Completed: | 20 May 2017 (last subject last visit) |
| NCT number: | NCT03066219 |
| Document Date | IRB approval on 06 February 2017 |
| Date of Report: | 11 September 2019 |

Statement of Compliance with
Good Clinical Practice

This study was performed in compliance with the ethical principles of the Declaration of Helsinki and the International Conference on Harmonisation (ICH) Harmonised Tripartite Guideline for Good Clinical Practice (GCP).

Confidentiality Statement

3. STUDY PROTOCOL

This was a multi-center, double-masked (participants and research team), randomized, placebo-controlled, phase 2 study conducted between February 2017 and May 2017 at 2 sites in the United States (Andover Eye Associates and Central Maine Eye Care). This study (ClinicalTrials.gov identifier: NCT03066219) was performed in compliance with the ethical principles of the Declaration of Helsinki and the International Conference on Harmonisation (ICH) Harmonised Tripartite Guideline for good clinical practice (GCP). Institutional Review Board (IRB)/Ethics Committee approval was obtained. All potential subjects provided written informed consent before screening.

After the screening visit, eligible subjects entered a one-week run-in period to receive preservative-free placebo solution bilaterally three times daily (TID) to minimize the placebo effect. Subjects that exhibited improvements in symptoms of dry eye syndrome (DES) at the end of the run-in period, relative to screening values, were disqualified. Eligible subjects were subsequently randomized in a 1:1 ratio to receive placebo or BRM421 Ophthalmic Solution three times daily (TID) in each eye for total 4 weeks, and the efficacy and safety assessments were performed at 1, 2 and 4 weeks after treatment.

4. STATISTICAL ANALYSIS PLAN

The primary efficacy analyses, including FCS and ocular discomfort score, were performed using the last observation carried forward (LOCF) imputation method of the intent-to-treat (ITT) population at week 4 for missing values. The treatment effect in each group was calculated by change from baseline in pre- to post-controlled adverse environment (CAE) mode.

The difference from baseline in pre- to post-CAE values for active treatment was tested versus placebo using a two-way ANCOVA model adjusting for baseline at $\alpha = 0.05$. A Wilcoxon rank sum test and a two-sample *t*-test were also assessed where appropriate.

The continuous and ordinal secondary efficacy variables were analyzed with an ANCOVA model adjusting for baseline and also evaluated with a two-sample *t*-test comparing active treatment to placebo. No imputation was performed for secondary efficacy variables.

All analyses were performed using SAS software, version 9.4 (SAS Institute Inc., Cary, NC, USA).

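### Two primary efficacy variables share one alpha of 0.05, and the plan does not say whether one or both must be significant or how the error rate is controlled

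*Combined protocol and SAP*

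**What the plan says.** Section 4, Statistical Analysis Plan, opens with "The primary efficacy analyses, including FCS and ocular discomfort score, were performed" and places these analyses in the "intent-to-treat (ITT) population at week 4 for missing values", with LOCF. The next paragraph sets the test and its level: "tested versus placebo using a two-way ANCOVA model adjusting for baseline at $\alpha = 0.05". It then adds: "A Wilcoxon rank sum test and a two-sample *t*-test were also assessed where appropriate".

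That is all the plan says about inference on the primary variables. No section states a success criterion, a testing order, a division of alpha or a multiplicity procedure. The plan does not say whether the tests are one- or two-sided. It does not say in words that each variable gets the full 0.05, although that is the natural reading of one alpha with no split.

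**The concern.** With more than one primary variable, an alpha of 0.05 has no fixed meaning until the plan says what counts as success. Under an either-endpoint rule, two tests at 0.05 give two chances of a false positive. Under a both-endpoints rule, the same two tests need no correction.

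The plan leaves both rules open. A reader of the results could take a win on one variable as a primary success at the 5% level, and nothing in the text rules that out. The rule could also be chosen after the p-values are known. What is at stake is whether a single-endpoint p-value between 0.025 and 0.05 can be reported as a positive primary result.

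**Working it through.** **Inputs from the documents**
- Primary variables: two are named (Section 4). The wording does not close the list at two.
- Alpha: 0.05, stated once (Section 4).
- Sample size: about 150, 75 per arm (Section 1), allocated 1:1 (Section 3).

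**Assumptions, because the documents are silent**
- Tests are two-sided.
- Each variable is tested at the full 0.05.
- The correlation ρ between the two test statistics is unknown, so a range is shown.

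**The plan's own figure.** Alpha of 0.05 is a design input. For a single test the false-positive rate is 1 − 0.95 = 0.05, as stated. There is no power statement to reproduce.

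**Rule A: either variable suffices, both nulls true**
- Independence: 1 − 0.95² = 1 − 0.9025 = 0.0975, which is 1.95 times 0.05.
- Upper bound at any correlation: 0.05 + 0.05 = 0.10.
- Correlated statistics: 1 − P(|Z₁| < 1.96 and |Z₂| < 1.96) for a standard bivariate normal.
- Favouring active only: 1 − P(Z₁ < 1.96 and Z₂ < 1.96). At independence this is 1 − 0.975² = 0.0494, against a nominal 0.025.

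**Rule B: both variables must be significant**
- Both nulls true: P(both) = 0.05 + 0.05 − P(either). At independence this is 0.10 − 0.0975 = 0.0025.
- If one variable truly responds, the joint claim is false only through the other. The error can then approach 0.05 but cannot exceed it.

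| ρ | Either, two-sided | Ratio to 0.05 | Either, favouring active | Ratio to 0.025 | Both, two-sided, both nulls true |
|---|---|---|---|---|---|
| 0 | 0.0975 | 1.95 | 0.0494 | 1.98 | 0.0025 |
| 0.3 | 0.0951 | 1.90 | 0.0476 | 1.91 | 0.0049 |
| 0.5 | 0.0907 | 1.81 | 0.0454 | 1.82 | 0.0093 |
| 0.7 | 0.0835 | 1.67 | 0.0417 | 1.67 | 0.0165 |
| 0.9 | 0.0704 | 1.41 | 0.0352 | 1.41 | 0.0296 |
| 1 | 0.0500 | 1.00 | 0.0250 | 1.00 | 0.0500 |

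**After adjustment.** With Bonferroni at 0.025 each, the familywise error is 1 − 0.975² = 0.0494 under independence and at most 0.05 at any correlation.

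**Power cost of testing at 0.025, 75 per arm.** In the normal approximation, the detectable effect is (z for alpha + z for power) × √(2/75):
- At 0.05: (1.960 + 0.842) × 0.1633 = 0.457 SD.
- At 0.025: (2.241 + 0.842) × 0.1633 = 0.503 SD.

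The noncentral t gives 0.460 and 0.508 SD. Put the other way, an effect with 80% power at 0.05 has about 71% power at 0.025, and one with 90% power has about 84%.

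**The case against.** The strongest counter-argument is that the inflation is conditional. The plan nowhere says that a win on either variable is a success. If the intended rule was that both must be significant, testing each at 0.05 is correct and the error is at most 5%. This stands. A reader might infer that the trial's chance of a false primary success is nearly double the stated alpha. The documents do not support that as a fact, because it needs an either-endpoint rule and independent or weakly correlated tests, and the plan states neither.

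The two-sided 9.75% also counts significant results that favour placebo, which are not successes. In the direction of interest the figure is about 4.9% against 2.5%. This stands for the absolute size. The relative inflation is about the same either way.

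Two further points lower the weight without closing the gap. The study is phase 2. The posted plan is also a short account in the past tense, so a fuller document may hold a rule that is not visible here.

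One might also object that a rule written now comes too late. Section 1 gives the last visit as 20 May 2017 and the report date as 11 September 2019. This stands against a fixed sequence chosen now: nothing in the documents puts FCS or ocular discomfort first, so such an order would not be prespecified. It does not stand against stating what rule existed, or against an adjustment that treats both variables alike.

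None of this supplies the missing rule. The plan attaches a formal alpha to a randomized, masked comparison and should say which claim that alpha governs.

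**Conclusion.** The gap is real: at least two primary variables, one alpha, no success rule and no multiplicity control. Because of it, the error rate of a primary claim is undetermined rather than demonstrably inflated.

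- If both variables must be significant, it is at most 5%.
- If either suffices, the two-sided familywise error lies between 5% (perfect correlation) and 10% (the bound): 9.75% under independence, 9.1% at correlation 0.5, 8.3% at 0.7 and 7.0% at 0.9.
- Counting only results favouring active, the either-endpoint rate is about 4.9% under independence and 4.5% at 0.5, against a nominal 2.5%.

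These figures assume two-sided tests at the full 0.05, exactly two primary variables, the ANCOVA as the deciding test, and both nulls true for the either-endpoint rates. The additional Wilcoxon and t-tests could add to the error if they may also decide success. That has not been quantified.

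**What to change.** 1. State the success rule that was set before unmasking, if there was one: either variable or both, with any order or alpha split. Confirm that the primary variables are these two only, that the ANCOVA decides, and whether the tests are two-sided.
2. If both had to be significant, say so. No adjustment is needed.
3. If no rule was set, say so and apply one symmetric procedure to the two ANCOVA p-values, disclosed as chosen afterwards:
   - Hochberg: claim both if both p ≤ 0.05; otherwise claim one only if its p ≤ 0.025.
   - Bonferroni: claim each only if its p ≤ 0.025.

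   The two procedures can differ only when the larger p-value lies between 0.025 and 0.05.
4. Label any other single-endpoint p-value, including those from the Wilcoxon and t-tests, as nominal.
5. Use a fixed sequence only if its order was set before unmasking.

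Cost: a few sentences and no new data. With 75 per arm, the effect detectable with 80% power on a single endpoint rises from 0.46 to 0.51 SD. Under Bonferroni this always applies. Under Hochberg it applies only when the other endpoint does not reach 0.05.

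### LOCF is the only missing-data method described for the week-4 primary analyses, with no justification and no sensitivity analysis; it can bias the treatment difference by an amount the documents leave unknown.

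*Combined protocol and SAP*

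**What the plan says.** Section 4 (Statistical Analysis Plan) covers "The primary efficacy analyses, including FCS and ocular discomfort score" and says they were run "using the last observation carried forward (LOCF) imputation method of the intent-to-treat (ITT) population at week 4 for missing values". The outcome is defined as follows: "The treatment effect in each group was calculated by change from baseline in pre- to post-controlled adverse environment (CAE) mode". The model is an ANCOVA adjusting for baseline. Section 4 adds: "A Wilcoxon rank sum test and a two-sample *t*-test were also assessed where appropriate". These change the test, not the treatment of missing values. For the secondary endpoints it says: "No imputation was performed for secondary efficacy variables".

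Section 3 (Study Protocol) says that "the efficacy and safety assessments were performed at 1, 2 and 4 weeks after treatment". It does not say whether the CAE challenge was run at weeks 1 and 2.

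The documents give no rationale for LOCF, no estimand, and no likelihood-based, multiple-imputation, observed-case or tipping-point analysis of the primary endpoints. They also do not say how many week-4 values were missing, how these split by arm, or whether a baseline value could be carried forward.

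**The concern.** LOCF fixes a subject who leaves early at the last recorded value. If scores are still moving, that value is out of date at week 4. The ANCOVA then counts it as a measurement, so the standard error carries no allowance for having guessed it.

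If benefit builds up over the four weeks, carried values hold only part of it and the estimated difference shrinks. If one arm loses more subjects, or loses them earlier, any change common to both arms is removed unevenly, and this can create or hide a difference. Because no other missing-data analysis is described, a reader cannot tell whether the primary result depends on LOCF.

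**Working it through.** **Inputs from the documents.** About 150 subjects, 75 per arm (title page); 1:1 allocation and visits at weeks 1, 2 and 4 (section 3); LOCF in the ITT set at week 4 and α = 0.05 (section 4). The sample size cannot be reproduced, because no power, effect size or SD is stated.

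**Assumed inputs.** Dropout shares pT (active) and pC (placebo); f, the share of the week-4 change already reached at the carried visit (f = 0 means that baseline is carried); m, the placebo change in SD; δ, the true difference in SD. Where δ is needed I use (1.960 + 0.842) × √(2/75) = 0.4575 SD. That is only a convenient scale (80% power, two-sided 0.05, both assumed).

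**Formula**, for dropout unrelated to outcome:

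bias = −(1 − f) × [pT(m + δ) − pC·m]

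**Equal dropout p.** The terms in m cancel, and the bias is −(1 − f)·p·δ, a relative loss of (1 − f)·p:

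| Dropout per arm | f = 0.5 | f = 0 |
|---|---|---|
| 2% | 1% | 2% |
| 5% | 2.5% | 5% |
| 10% | 5% | 10% |

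**Unequal dropout, true effect 0.4575 SD, m = 0.5.**
- 15% active vs 5% placebo, f = 0: −(0.15 × 0.9575 − 0.05 × 0.5) = −0.119 SD, or −26%. With f = 0.5: −0.059 SD, or −13%.
- 5% active vs 15% placebo, f = 0: −(0.05 × 0.9575 − 0.15 × 0.5) = +0.027 SD, or +6%. With f = 0.5: +0.014 SD, or +3%.

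**No true effect.** The bias is −(pT − pC)(1 − f)m. For 15% vs 5%:
- f = 0.25, m = 0.5: 0.10 × 0.75 × 0.5 = 0.0375 SD.
- f = 0, m = 0.8: 0.10 × 1 × 0.8 = 0.08 SD.
- It is zero if m = 0 or if dropout is equal in rate and timing.

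**Timing alone.** Suppose 10% drop out in each arm and m = 0.5, but active dropouts carry baseline (f = 0) and placebo dropouts carry a half-way value (f = 0.5). With no true effect the bias is −(0.10 × 1 × 0.5 − 0.10 × 0.5 × 0.5) = −0.025 SD.

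**Simulation.** 75 per arm, 600 runs per scenario, m = 0.5, with 40%, 70% and 100% of the change reached at weeks 1, 2 and 4. Visit correlations were 0.5 to 0.65. Dropout was more likely after a worse last value (MAR).

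| Dropout active / placebo, value carried | LOCF estimate (true 0.4575) | MI estimate | LOCF rejection, no effect | MI rejection, no effect |
|---|---|---|---|---|
| 5% / 5%, week 1 | 0.450 | 0.457 | 3.8% | 4.0% |
| 10% / 10%, week 1 | 0.436 | 0.454 | 4.3% | 4.5% |
| 10% / 10%, baseline | 0.414 | 0.463 | 5.3% | 3.7% |
| 15% / 5%, baseline | 0.309 | 0.462 | 9.2% | 5.5% |
| 5% / 15%, baseline | 0.526 | 0.467 | 7.3% | 4.3% |

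The Monte Carlo standard error at a 5% rejection rate is √(0.05 × 0.95/600) = 0.9 points. With balanced dropout, LOCF showed no clear inflation of the error rate. With a 10-point imbalance it did. The simulation's dropout mechanism is one under which MI is valid, so it favours MI by construction.

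**The case against.** The best defence is that the bias may be trivial. In a four-week trial with 2 to 5% balanced dropout, LOCF costs 1 to 5% of the effect, always toward no effect, and under the null it costs nothing. That is correct. The documents give no dropout figure, however, so they support neither this reassurance nor alarm.

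Four stronger readings are tempting but are not supported:

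- *The protocol expects a placebo response, so carried values must be out of date.* Section 3 describes a placebo run-in meant to reduce that response, with subjects whose symptoms improved disqualified. The endpoint is also a pre-to-post-CAE difference, so a shift common to both readings cancels. The run-in neither establishes nor excludes later drift, and the 0.5 to 0.8 SD common change is purely an assumption.
- *LOCF costs the trial several points of power.* At an assumed 0.460 SD (80% by a t-based calculation), 5 to 7.5% attenuation gives 75.9 to 73.6%. Simply losing 10% of subjects (67.5 per arm) already gives 75.7%, so most of that drop comes from missingness itself.
- *A difference of about 0.46 SD is what the trial was designed to detect.* No design effect is stated.
- *Every dropout was scored as zero change.* That would follow only if baseline was carried, for example because CAE was run only at baseline and week 4. The documents do not settle this.

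Two further objections stand. MMRM and multiple imputation rest on MAR, which cannot be verified either. And the last visit was on 20 May 2017, so a new primary analysis now would be post hoc. The SAP section is also a brief account in the past tense: other analyses may have been run, and the point is that none is described.

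**Conclusion.** The point holds as a possible bias of unknown size. LOCF is the sole described method for both named primary endpoints, unjustified and unchecked. Under assumed inputs the distortion runs from 1 to 2% of the effect (2% dropout per arm), through 5 to 10% (10% per arm, f from 0.5 to 0), to a false difference of about 0.04 to 0.08 SD under no true effect (15% vs 5% dropout, common change 0.5 to 0.8 SD). The sign is toward no effect with balanced dropout and growing benefit; with unequal dropout and drift it can go either way. A reader might infer that the reported difference is biased, but that needs dropout by arm, its timing and the time course of scores, none of which is given.

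**What to change.** 1. Report the number of missing week-4 values for each primary endpoint by arm, timing and reason. State which value was carried forward, and whether baseline could be.
2. If pre- and post-CAE scores exist at weeks 1 and 2, analyse the ITT set with an MMRM: treatment, visit, treatment-by-visit, baseline, baseline-by-visit and site, with unstructured covariance, reading the week-4 contrast.
3. If those scores exist only at baseline and week 4, use multiple imputation by arm from the baseline CAE values and whatever week 1 and 2 scores are available, then ANCOVA combined by Rubin's rules.
4. Add one control-based imputation as a check on departure from MAR.

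In a plan written before unmasking, the analysis in step 2 or 3 should be primary, with LOCF as a sensitivity analysis. For this completed trial, report the new analyses beside the LOCF result and label them post hoc.

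The cost is some extra programming and no new data. The price is reliance on MAR and possibly a slightly wider confidence interval.

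### The 'two-way' primary ANCOVA leaves its second factor unnamed and the secondary ANCOVA is baseline-only as written, so site may be costing precision in a two-site trial

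*Combined protocol and SAP*

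**What the plan says.** Section 4 (Statistical Analysis Plan) gives two parametric models.

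- **Primary endpoints** (FCS and ocular discomfort at week 4): the change from baseline in the pre- to post-CAE difference was "tested versus placebo using a two-way ANCOVA model adjusting for baseline", at an alpha of 0.05. Supporting tests follow: "A Wilcoxon rank sum test and a two-sample *t*-test were also assessed where appropriate".
- **Secondary endpoints**: "The continuous and ordinal secondary efficacy variables were analyzed with an ANCOVA model adjusting for baseline", and they were "also evaluated with a two-sample *t*-test comparing active treatment to placebo".

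Section 3 (Study Protocol) says that the trial was run "at 2 sites in the United States", with 1:1 randomisation. Neither section names site as a model term, a stratification factor or the subject of a sensitivity analysis.

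**The concern.** The label on the primary model and the terms listed for it do not match. Baseline is a covariate, so treatment is the only classification factor that can be identified. Either a second factor was fitted and not named, or the label is wrong. At least two models fit the wording, treatment + baseline and treatment + site + baseline, and they can give different p-values for the same data. A primary test should have one reading.

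The secondary model does not carry the two-way label and, as written, has no site term. No reason is given for the difference from the primary model.

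What is at stake is precision. If the two sites differ in the outcome after baseline adjustment, a model without site counts that difference as noise, and the confidence interval for the treatment effect is wider than it need be.

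**Working it through.** **1. Terms set side by side**

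| Model | Label | Named besides treatment | Site |
|---|---|---|---|
| Primary | two-way ANCOVA | baseline | not named; could be the second factor |
| Secondary | ANCOVA | baseline | not named; absent as written |

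**2. The plan's own figure.** The title page gives about 150 subjects, 75 per arm. No effect size, SD, power or dropout is stated, so this number cannot be reproduced. Solving backwards, with two-sided alpha 0.05 assumed because sidedness is not stated, the detectable standardised difference is

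d = (z₀.₉₇₅ + z_power) × √(2/75)

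- 80% power: (1.9600 + 0.8416) × 0.1633 = 0.4575
- 90% power: (1.9600 + 1.2816) × 0.1633 = 0.5293

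**3. What omitting site costs.** Let R² be the share of the baseline-adjusted outcome variance due to site. It is an assumption, since the documents give no value. Adding site multiplies the residual SD by √(1 − R²). If power without site is 80%, power with site is Φ(2.8016/√(1 − R²) − 1.9600).

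| Assumed R² | Power with site | Points lost by omission | n per arm for 80% with site | SE ratio, without/with site |
|---|---|---|---|---|
| 0 | 80.0% | 0 | 75 | 1.000 |
| 0.05 | 82.0% | 2.0 | 72 | 1.026 |
| 0.10 | 84.0% | 4.0 | 68 | 1.054 |
| 0.20 | 88.0% | 8.0 | 60 | 1.118 |

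From a 90% base, power with site is 91.4%, 92.7% and 95.2% at R² of 0.05, 0.10 and 0.20.

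**4. The same on the scale of a site difference.** For a difference of D residual SDs and a share p of subjects at one site, the between-site variance is v = D²p(1 − p). The equivalent loss out of 150 subjects is 150 × v/(1 + v).

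- 50:50 split, D = 0.3, 0.5, 0.8: v = 0.0225, 0.0625, 0.16; loss 3.3, 8.8, 20.7 subjects; R² = v/(1 + v) = 0.022, 0.059, 0.138.
- 80:20 split, same D: v = 0.0144, 0.04, 0.1024; loss 2.1, 5.8, 13.9 subjects.
- D = 0: no loss.

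The equal split is the worst case, because p(1 − p) is largest at 0.5. Both splits and all values of D are assumptions.

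**5. Type I error.** This was checked by simulation: N = 150, two equal sites assumed, 10,000 runs per setting, baseline-only ANCOVA.

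| Assumed R² | Unstratified allocation | Allocation balanced by site |
|---|---|---|
| 0 | 0.050 | 0.050 |
| 0.05 | 0.053 | 0.043 |
| 0.10 | 0.049 | 0.039 |
| 0.20 | 0.051 | 0.029 |

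The simulation standard error is about √(0.05 × 0.95/10,000) = 0.002. The error rate stays at about 5% without stratification and falls below 5% with it. Simulated power under unstratified allocation agrees with step 3: 79.1% without site against 81.1% with it at R² = 0.05, and 78.9% against 82.8% at R² = 0.10.

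**6. Price of adding site.** Error degrees of freedom go from 150 − 3 = 147 to 146, and the critical t from 1.9762 to 1.9763. This takes all 150 as analysed; secondary variables were not imputed, so their counts may be lower.

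**The case against.** The strongest reply is that the text is a short past-tense summary, in a report dated September 2019, of a trial that ended in May 2017. A terse sentence shows that the description is incomplete; it is weak evidence that a term was left out. Three further arguments support this.

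- **Site may be the second factor.** In a two-site trial it is the obvious candidate. A reader might infer that site was left out of the primary model, but the text neither includes nor excludes it. This stands in full. The same caution applies, less strongly, to the secondary model: the phrase about adjusting for baseline did not list every term of the primary model, so it may not do so there either. Baseline-only remains the natural reading of the secondary sentence.
- **The endpoint removes much of a site shift.** The primary outcome is a change from baseline in a pre- to post-CAE difference. A constant grading shift at one site cancels from pre to post. A constant site difference in response to CAE cancels in the change from baseline; once baseline is also a covariate, the fraction (1 − baseline slope) remains. This makes a large residual site effect less likely for the primary endpoints. Section 4 describes that construction for the primary analysis only. The documents also do not say who grades FCS or how CAE is delivered at each site, so no mechanism for a site difference can be read from them.
- **Validity is not at risk.** This stands. A reader might infer a false-positive problem, and the simulation shows none.

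A reader might also take 'two-way' to imply a fitted interaction, so that the treatment p-value no longer refers to an average effect. Nothing in section 4 suggests an interaction. The argument would apply to a treatment-by-baseline term with uncentred baseline; with treatment by site, the usual SAS Type III test averages over sites.

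What the reply does not remove is that the primary model has an unidentified factor, and that the secondary model as written omits a recorded variable that costs almost nothing to include.

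**Conclusion.** The point holds in a limited form. The primary model is under-specified, and omission of site from it is not established. For the secondary model, omission is what the text says. Where site is absent, the consequence is some loss of precision if the sites differ, with type I error at or below its nominal level. The conservative case needs allocation balanced by site, and section 3 states only a 1:1 ratio.

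The loss runs from nothing to about 4 power points for an assumed site share of 0% to 10% of residual variance, and reaches about 8 points only at 20%. These figures rest on an assumed 80% base, two-sided testing at 0.05 and 75 analysed per arm. They illustrate a range and do not estimate what happened in this trial.

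**What to change.** Name both factors of the two-way ANCOVA. State whether site was in the primary model and in the secondary model, and whether randomisation was stratified by site.

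Specify one model for primary and secondary variables: outcome = treatment + site (2 levels, fixed) + baseline, main effects only. Report the treatment difference from it with a 95% CI.

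The trial is complete, so the status of this model depends on the original plan. If that plan already included site, the text only needs correcting. If it did not, keep the original model in its place and report the site-adjusted result beside it, labelled as a sensitivity (post hoc) analysis.

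The cost is one error degree of freedom and a small amount of extra analysis. Site is already recorded, so no new data are needed.

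### The supportive Wilcoxon test on the primary endpoints omits the ANCOVA's baseline covariate, so it may differ from the ANCOVA for reasons unrelated to non-normality; a baseline-adjusted rank test would serve better.

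*Combined protocol and SAP*

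**What the plan says.** All the relevant text is in section 4 (Statistical Analysis Plan).

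- **Quantity analysed.** "The treatment effect in each group was calculated by change from baseline in pre- to post-controlled adverse environment (CAE) mode". Baseline is therefore already subtracted from the outcome.
- **Endpoints and population.** FCS and ocular discomfort score at week 4, ITT, with LOCF.
- **Main test.** Active treatment is "tested versus placebo using a two-way ANCOVA model adjusting for baseline", at alpha 0.05. The second factor of the two-way model is not named, nor is it said which baseline measure is the covariate.
- **Supportive tests.** "A Wilcoxon rank sum test and a two-sample" t-test, used as judged appropriate. No covariate is mentioned. No purpose is given, and nothing is said about what follows if they differ from the ANCOVA.
- **Secondary variables.** Continuous and ordinal variables get the same pairing of a baseline-adjusted ANCOVA with a two-sample t-test.

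**The concern.** The primary endpoints are scores, so a reader will want to know whether the ANCOVA result depends on normal theory. The Wilcoxon is the only primary-endpoint test in the plan that could help answer this. As named, however, it removes the normality assumption and the covariate together.

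Subtracting baseline is not the same as adjusting for it. A change score fixes the slope on baseline at 1, whereas the ANCOVA estimates it. When the correlation between baseline and week 4 is below 1, the change score carries more error variance.

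A significant ANCOVA beside a non-significant Wilcoxon could therefore reflect distribution, the missing covariate, or both, and the reported tests would not separate them. The t-test on change keeps the normal-theory assumption and drops the covariate, so it does not address the distributional question.

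**Working it through.** **Inputs from the documents.** Section 1 (Title Page) describes a "phase 2 CAE study in approximately 150 subjects. (75 per treatment arm"). Section 3 (Study Protocol) gives 1:1 allocation. Section 4 gives alpha 0.05.

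**Assumptions, because the documents are silent.** Two-sided alpha; ANCOVA power 80% (90% as a check); correlation rho from 0 to 0.9; equal variances at baseline and week 4; the covariate is the baseline value of the same pre- to post-CAE measure; normal data.

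**The plan's own figure.** The 75 per arm cannot be reproduced, since no effect, SD or power is stated. Back-solving, the detectable difference is (1.960 + 0.842) × √(2/75) = 0.457 residual SD at 80% power, and 0.529 at 90%.

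**Variance.** With σ the SD at each time:
- ANCOVA residual variance: σ²(1 − rho²)
- change-score variance: 2σ²(1 − rho)
- ratio, change to ANCOVA: 2(1 − rho)/(1 − rho²) = 2/(1 + rho), above 1 for every rho below 1

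**Power.** Fix the effect so that the ANCOVA has 80% power (2.802 = 1.960 + 0.842).
- t-test on change: Φ(2.802 × √((1 + rho)/2) − 1.960)
- Wilcoxon on change: the same, with (1 + rho)/2 multiplied by 3/π = 0.955, the rank test's large-sample efficiency under normality

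At rho 0.5 the t-test has Φ(2.802 × √0.75 − 1.960) = Φ(0.466) = 67.9%. The Wilcoxon has Φ(2.802 × √(0.955 × 0.75) − 1.960) = Φ(0.411) = 65.9%.

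| rho | 2/(1+rho) | t-test power, % (loss) | Wilcoxon power by formula, % (loss) | Wilcoxon loss, simulated |
|---|---|---|---|---|
| 0.1 | 1.82 | 54.7 (25.3) | 52.8 (27.2) | about 28 |
| 0.3 | 1.54 | 61.7 (18.3) | 59.8 (20.2) | about 20 |
| 0.5 | 1.33 | 67.9 (12.1) | 65.9 (14.1) | about 15 |
| 0.7 | 1.18 | 73.3 (6.7) | 71.4 (8.6) | about 8 |
| 0.9 | 1.05 | 78.0 (2.0) | 76.1 (3.9) | about 4 |

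Only about 2 points of each Wilcoxon loss come from using ranks; the rest comes from the missing covariate. If the ANCOVA has 90% power, the t-test losses shrink to 19.1 points at rho 0.2, 9.8 at 0.5 and 5.2 at 0.7.

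**What an adjusted rank test keeps.** If only the cost of ranking remains, power is Φ(2.802 × √0.955 − 1.960) = Φ(0.778) = 78%. In simulation, a rank sum test on the residuals from the baseline regression kept 77–79% at every rho tried from 0.1 to 0.9. A Quade rank ANCOVA compares with the plain Wilcoxon as follows.

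| rho | Power: Wilcoxon, Quade | Verdict differs from ANCOVA: Wilcoxon, Quade |
|---|---|---|
| 0.3 | 61%, 78% | 24%, 6% |
| 0.5 | 66%, 77% | 19%, 7% |
| 0.7 | 71%, 75% | 13%, 8% |

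These data are exactly normal, so none of the disagreement signals a distributional problem. At rho 0.9 Quade loses its advantage (72% against 75% for the plain Wilcoxon).

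**Under the null.** The ANCOVA, t-test and Wilcoxon each rejected in about 5% of simulated trials (range 4.6% to 5.6% over rho 0.2 to 0.8).

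**The case against.** The strongest reply is that little turns on this. The ANCOVA is the main test, and its estimate, power and type I error are untouched. The unadjusted tests are valid under randomization. No result is reported, and even at rho 0.3 the Wilcoxon and ANCOVA agree in about three-quarters of the simulated trials. All of this stands, and it limits the point to the reading of a supportive test.

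Several stronger readings are tempting but unsupported:

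- **A fixed loss of power.** A reader might quote one range, such as 9 to 21 points, for both tests. That range fits the Wilcoxon alone, over rho 0.3 to 0.7 with ANCOVA power near 80%. The documents supply neither figure. The t-test loss alone runs from 29 to 2 points over rho 0 to 0.9.
- **Baseline ignored altogether.** The analysed quantity is a change from baseline; only the regression covariate is missing.
- **A failed robustness check.** Section 4 never gives these tests that role.
- **Disagreement mostly due to the covariate.** This is reasonable at rho 0.3 to 0.5. At 0.7 an adjusted rank test still differs from the ANCOVA in 8% of trials, against 13%, so the statement does not hold generally.
- **A useless t-test.** It shows the unadjusted difference and needs no linear covariate model. Deleting it is a matter of preference.

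**Conclusion.** The point holds in a limited form. The supportive Wilcoxon differs from the ANCOVA in two respects, so disagreement between them **may** arise for reasons unrelated to non-normality. The direction is certain for any rho below 1 under the equal-variance, same-measure assumptions. The size is not known: about 28 points of Wilcoxon power at rho 0.1, falling to 4 at rho 0.9, if the ANCOVA has about 80% power with 75 per arm.

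The documents do not support inferring that the primary analysis is invalid or underpowered, or that the tests did in fact disagree. What can be gained is a supportive test that is more precise and easier to interpret, using a baseline already collected.

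**What to change.** Make the supportive rank test baseline-adjusted, on the same ITT/LOCF subjects and the same covariates as the ANCOVA, including the second factor once it is named. There are two options:

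- **Quade rank ANCOVA:** rank the week-4 and baseline measures, regress one set of ranks on the other, and compare the residuals by arm.
- **Rank sum test on residuals:** regress on baseline without the treatment term, then apply the Wilcoxon to the residuals. This is the safer choice if the correlation may be very high, because its power did not depend on rho.

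Name one option before running it. Section 1 shows the last subject's last visit in May 2017, so report it as an added, labelled post hoc analysis, and use the wording prospectively in any later SAP. The t-test may stay for primary and secondary variables if labelled as an unadjusted comparison.

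The cost is a few lines in the SAS software already used, with no new data and no patient burden. The downside is that a rank test gives no effect estimate on the score scale; the ANCOVA still supplies that.
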